6.3.2.1 Blinding of trial subjects

All trial subjects in Cohorts 1 to 4 will be blinded to their assigned trial treatments as described in the SoA in Section [1.3](#).

6.3.2.2 Blinding of trial site personnel

The trial staff dispensing and administering the vaccine will be unblinded, but all other trial personnel, including the principal investigator, will be blinded as described in the SoA in Section [1.3](#). The principal investigator will assign the responsibility of unblinded dispenser and unblinded administrator to persons who will not participate in the evaluation of any trial subject. More than one unblinded dispenser/administrator may be assigned. A member of the trial site personnel or clinic pharmacy should fulfill this role. Contact between the unblinded dispenser/administrator and trial subjects should be kept to a minimum.

The investigator, trial coordinator, and any site staff other than the unblinded dispenser/administrator must not be allowed to know the investigational product assigned to any trial subject and must not be allowed to see the investigational product containers.

BNT162b4 and BNT162b2 Bivalent do not differ in physical appearance but the trial treatments differ slightly in volume (and thus could lead to unblinding, e.g., when administering the IMP or recording the administered IMP volume), details of the trial treatment blinding measures will be provided in the Blind Management Plan.

The trial may be unblinded to site personnel at timepoints as decided by the sponsor.

6.3.2.2.1 *Unblinding of trial subjects*

In case of an emergency, the investigator has the sole responsibility for determining if unblinding of a trial subject's trial treatment assignment is warranted. Trial subject safety must always be the first consideration in making such a determination. Prior to the trial start, the investigator will be provided with guidance relevant to the emergency unblinding procedure.

If the investigator decides that unblinding is warranted to ensure the safety of a trial subject, the investigator should make every effort to contact the sponsor prior to unblinding the trial subject's trial treatment assignment unless this could delay further management of the trial subject.

If a subject's trial treatment assignment is unblinded, the sponsor must be notified within 24 h after breaking the blind. The date and reason that the blind was broken must be recorded in the source documentation and case report form (CRF).

6.3.2.3 Blinding of laboratory personnel

In this trial, the laboratory personnel at internal or external laboratories may be unblinded to support rolling snapshot analyses. For further details relevant to the unblinding of these laboratory personnel, see the Blind Management Plan.

6.3.2.4 Blinding of IRC members

To enable the IRC to provide real time medical oversight of trial subject safety during the conduct of this trial, the IRC members will include unblinded sponsor staff. For further details about the IRC, see Section [10.1.5](#).

6.3.2.5 Blinding of sponsor personnel

Relevant sponsor personnel will be unblinded to trial treatment allocation for the subjects. However, sponsor personnel who routinely have contact with blinded site personnel and the functions responsible for the daily CRO oversight will be blinded. Further details, see the Blind Management Plan.

6.4 Trial treatment compliance

Trial subjects will receive trial treatment directly from the (unblinded) investigator or a designee under medical supervision. The date and time of each dose administered must be recorded in the source documents and in the CRF. The dose of trial treatment and subject identification number will be confirmed at the time of dosing by a member of the trial site personnel other than the person administering the trial treatment.

See Section 8.4 for guidance on the treatment of overdose or errors in drug administration.

6.5 Concomitant therapy

6.5.1 Prohibited concomitant therapies during the trial

(See #6 in the [inclusion criteria for Cohorts 1 to 4](#) and #6 in the [inclusion criteria for Cohort 5](#)) Trial subjects should not have been vaccinated with:

- Non-trial vaccines (except COVID-19 vaccines) starting 28 d prior to Dose 1 and until 28 d after receiving of the last IMP dose (Dose 2). Seasonal influenza vaccine is allowed, however it should be given at least 14 d before or after any administration of IMP.
- Non-trial COVID-19 vaccines until 6 months (168 d) post last IMP dose for Cohorts 1 to 4 and until 28 d post last IMP dose for Cohort 5.
Subjects in Cohorts 1 to 4 that continue to Dose 2 should not have been vaccinated with non-trial COVID-19 vaccines, starting at least 90 d prior to Visit 1 and until completion of the subject's last trial visit.

(See #7 in the [exclusion criteria for Cohorts 1 to 4](#) and #7 in the [exclusion criteria for Cohort 5](#)) Throughout the entire trial, trial subjects should not receive radiotherapy or immunosuppressive therapy, including cytotoxic agents or systemic corticosteroids (if systemic corticosteroids are administered for ≥ 14 d at a dose of ≥ 20 mg/d of prednisone or equivalent), e.g., for cancer or an autoimmune disease, or planned receipt throughout this trial. Inhaled/nebulized (except high doses as per #3a in the [exclusion criteria for Cohorts 1 to 4](#) and #3a in the [exclusion criteria for Cohort 5](#)), intraarticular, intrabursal, or topical (skin or eyes) corticosteroids are permitted.

(See #8 in the [exclusion criteria for Cohorts 1 to 4](#) and #8 in the [exclusion criteria for Cohort 5](#)) Trial subjects should not receive any blood/plasma products and/or immunoglobulin containing therapy (including monoclonal antibodies) from Visit 0 or prior to Dose 2 until 120 d after the last IMP administration for Cohorts 1 to 4, or until 90 d after the last IMP administration for Cohort 5.

(See #9 in the [exclusion criteria for Cohorts 1 to 4](#) and #9 in the [exclusion criteria for Cohort 5](#)) Trial subjects should not receive allergy treatment within 14 d after any visit with IMP administration in this trial.

6.5.2 *Permitted concomitant therapies during the trial*

Seasonal influenza vaccine is allowed; however, it should be given at least 14 d before or after any administration of trial IMP.

The use of antipyretics and other pain medication to treat symptoms after IMP administration or for ongoing conditions is permitted, but not to prevent symptoms associated with IMP administration (i.e., up to 12 h before each IMP administration).

Administration of standard therapeutic dose of acetaminophen (preferable), or a non-steroidal anti-inflammatory drug (NSAID) if acetaminophen is contraindicated is permitted (paracetamol / acetaminophen at doses of up to 4 g/d).

Inhaled, topical, or localized injections of corticosteroids (e.g., intraarticular or intrabursal administration) are permitted.

Other concomitant medication may be considered on a case-by-case basis by the investigator, if considered necessary after consultation with the trial Medical Monitor.

6.5.3 *Recording of concomitant therapy during the trial*

All concomitant medications used (permitted or prohibited, including over the counter or prescription medicines, vitamins, and/or herbal supplements) during the periods defined in the SoAs (Section 1.3 and Section 13.5) must be recorded in the CRF along with:

- The reason for use
- Dates of administration including start and end dates
- Dosage information including dose and frequency

The trial Medical Monitor should be contacted if there are any questions regarding concomitant or prior medication.

6.6 *Dose modifications*

The trial design follows a structured dose escalation schema. For details, see Section 4.1.

Dose escalation decisions to the next DL and DL modifications (i.e., dropping the DL to the previous acceptable DL or to an 'in-between' DL) will be confirmed by the IRC.

Cohort DL escalations: dose escalation will only continue if the safety and tolerability of the previous DL was considered acceptable by the IRC and no stopping/pausing rules were met.

Other unplanned dose modifications, pausing (temporary halting) of trial treatment, or even discontinuation of trial treatment may be required. See Section 7.1 for guidance on criteria for such cases.

6.7 *Access to trial treatment after the end of the trial*

Provision of access to trial treatment after the end of the trial is not planned.

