5.1 Inclusion criteria

5.1.1 *Inclusion criteria – Cohorts 1 to 4*

Volunteers are eligible to be included in the trial if all of the following criteria apply:

- 1 Have given informed consent by signing and dating the informed consent form (ICF) before initiation of any trial-specific procedures.
- 2 Are willing and able to comply with scheduled visits, treatment schedule, laboratory tests, lifestyle restrictions, e.g., to follow good practices to reduce their chances of being infected or spreading COVID-19, and other requirements of the trial. This includes that they are able to understand and follow trial-related instructions.
- 3 Are aged 18 yrs and older at randomization, have a body mass index over 18.5 kg/m² and under 35 kg/m², and weigh at least 50 kg at Visit 0.
- 4 Are healthy, in the clinical judgment of the investigator based on volunteer-reported medical history data, and physical examination, 12-lead electrocardiogram (ECG), vital signs, and clinical laboratory test outcomes at Visit 0.

Note: Healthy volunteers with pre-existing stable disease (e.g., obesity), defined as disease not requiring significant change in therapy or hospitalization for worsening disease during the 84 d before Visit 0, can be included.

5 Agree not to enroll in another trial with an IMP starting from Visit 0 and until 168 d after receiving the last IMP dose.

Inclusion criteria pertaining to Dose 2: If 168 d after the subject's first IMP dose had passed before they consent to Dose 2, they should agree to not enroll in another trial from the time of consent to Dose 2 until 168 d after receiving Dose 2 of the IMP.

6 Agree not to be vaccinated with:

- Non-trial vaccines (except COVID-19 vaccines, as per next sub-bullet) starting 28 d prior to the Dose 1 and until 28 d after receiving of the last IMP dose. Seasonal influenza vaccine is allowed; however, it should be given at least 14 d before or after any administration of IMP.

Inclusion criteria pertaining to Dose 2: If 28 d after the subject's first IMP dose had passed before they consent to continue Dose 2, they should not have been vaccinated with non-trial vaccines starting from the time of consent to Dose 2 and until 168 d after receiving the Dose 2 of the IMP.

- Non-trial COVID-19 vaccines starting at least 90 d prior to the Visit 1 and until completion of the subject's last trial visit.

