6.3 Measures to minimize bias: randomization and blinding

Cohorts 1, 2, 3a, 3b, 4a, and 4b are observer-blind for Dose 1, through Visit 5 only. Since only prior recipients of BNT162b4 will receive Dose 2, Dose 2 will be open-label. Trial subjects will be permitted to be unblinded from Visit 5.

Cohort 5 is single arm and open-label for Dose 1 and Dose 2.

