#### Immunogenicity Per Protocol Set

All participants included in the Immunogenicity Analysis Set, that have no major protocol deviations (PDs) that can confound immunogenicity data. A participant will only be excluded from the Immunogenicity Per Protocol Set if the participant had an important protocol deviation that can confound all immunogenicity data as determined by the sponsor. If a participant has an important protocol deviation that can confound subsequent immunogenicity data as determined by the sponsor then the participant will remain in the Immunogenicity Per Protocol Set, and only samples before the event will be included in the analysis.

Participants who have positive central or local nucleic acid amplification-based test (NAAT) result at pre-Dose 1 will be excluded from Immunogenicity Per Protocol Set since active infection indicated by positive NAAT at pre-Dose 1 may impact immunogenicity assessments post dose even though this is not a protocol deviation.

For immunogenicity analyses, the sampling windows with grace periods specified in [Table 4](#) will be used to define the valid samples for analysis sets. The samples drawn within the visit specific window with grace period will be valid for immunogenicity analysis in both the Immunogenicity Analysis Set and the Immunogenicity Per Protocol Set. Immunogenicity Per Protocol Set will be used for secondary and [CCI](#) endpoints in the BNT162-21 trial. Immunogenicity Analysis Set will not be used for immunogenicity analyses as the analyses based on Immunogenicity Per Protocol Set will serve the objectives of the study.

Only participants without breakthrough SARS-CoV-2 infections (without positive central or local NAAT results from pre-Dose 1 through the visit) will be analyzed for the respective visit.

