## 5.2 Protocol deviations

Protocol deviations are failures to adhere to the inclusion/exclusion criteria and protocol requirements. Important protocol deviations are a subset of protocol deviations that may significantly impact the completeness, accuracy, and/or reliability of key study data or that may significantly affect a participant's rights, safety, or well-being. Protocol deviations (PDs) will be classified into key PDs (important) and non-key PDs. Key PDs that lead to participant/sample exclusion from the immunogenicity analyses will be identified and provided for incorporation into the analysis datasets prior to database lock.

All PDs will be assessed and documented prior to releasing the database. Depending on the nature of the key PD, either the whole participant data might be excluded from the analysis sets (i.e., for key deviations on ICF), or only the data collected after the key PD

occurred might be excluded (e.g., for use of prohibited concomitant medications during the trial).

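### Protocol 6.5.1 ends the outside COVID-19 vaccine bar earlier than the inclusion criterion it cites, for one-dose participants only, and the SAP leaves the affected Month 6 samples to sponsor judgement

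*Protocol*

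**What the plan says.** Protocol 5.1.1, inclusion criterion 6, has every Cohort 1 to 4 participant agree not to receive "Non-trial COVID-19 vaccines starting at least 90 d prior to the Visit 1 and until completion of the subject's last trial visit".

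Protocol 6.5.1 refers back to that criterion but gives a different end point: "Non-trial COVID-19 vaccines until 6 months (168 d) post last IMP dose for Cohorts 1 to 4". Its next sentence restores the last-visit limit for one subgroup: "Subjects in Cohorts 1 to 4 that continue to Dose 2 should not have been vaccinated with non-trial COVID-19 vaccines", from 90 d before Visit 1 to the last trial visit.

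Protocol 6.3 fixes who can be in that subgroup: "Since only prior recipients of BNT162b4 will receive Dose 2, Dose 2 will be open-label". Controls are therefore one-dose by design, and Visit 6 is their last visit.

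SAP Table 7 lists ancestral and BA.4/5 neutralizing titers at Visit 6 for all of Cohorts 1 to 4, and XBB.1.5 as well in Cohorts 3 and 4. SAP Table 4 accepts a Month 6 sample up to Day 197.

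SAP 5.1 deals with events that spoil later samples as follows: "If a participant has an important protocol deviation that can confound subsequent immunogenicity data as determined by the sponsor", the participant stays in the set and "only samples before the event will be included in the analysis". SAP 5.2 supplies the definition: "Protocol deviations are failures to adhere to the inclusion/exclusion criteria and protocol requirements". It adds that data collected after a key deviation might be left out, and its example is use of a prohibited concomitant medication. Infection is handled without any such judgement: a participant is analyzed at a visit only if "without positive central or local NAAT results from pre-Dose 1 through the visit".

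**The concern.** A spike vaccine taken shortly before Visit 6 can raise the titers measured there. Two protocol sections disagree on whether a one-dose participant may take one, and the disagreement follows treatment arm: under 6.5.1 every control is released and no Dose 2 recipient is. If participants or sites followed 6.5.1, any effect on the Month 6 titers could differ between treatment groups.

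The SAP has a way to remove such a sample, but it runs through a decision that the event was an important deviation. That decision is harder to predict when the protocol's own list of prohibited therapies no longer covers the event. In the visible SAP text, the sampling window and a positive NAAT are the only visit-level exclusions that need no such decision.

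**Working it through.** **Inputs**
- Bar: 168 d after the last dose, also described as 6 months (Protocol 6.5.1).
- Dose 1 is trial Day 1; one month is 30.4375 d (SAP 6.1.2).
- Visit 6: Day 180, window -10 d to +30 d (Protocol 1.3, Table 3).
- Month 6 sample valid from Day 163 to Day 197 with the grace period. The waiver of that window covers pre-Dose 2 draws only (SAP Table 4 and footnote).
- 45 BNT162b4 recipients and 15 controls in each of six cohorts (Protocol Table 2).

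**The plan's own figure.** 6 × 28 d = 168 d, so the stated figure uses 28-day months. With the SAP's month, 6 × 30.4375 = 182.6 d.

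**Timing on the 168 d reading**
- Last barred day: 1 + 168 = Day 169. First free day: Day 170.
- Visit 6 window: 180 - 10 = Day 170 to 180 + 30 = Day 210.
- In-window Visit 6 draws that are also SAP-valid: Day 170 to 197.
- Longest time from vaccine to valid sample: 197 - 170 = 27 d. At target Day 180: 180 - 170 = 10 d.

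**Timing on the six-month reading**
- The bar ends at 1 + 182.6 = 183.6, so the first free day is Day 184.
- Longest time: 197 - 184 = 13 d. At target Day 180 there is none, and draws on Day 170 to 183 lie inside the bar.

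**Who is released by 6.5.1**
- Controls: 6 × 15 = 90 of 90.
- BNT162b4 recipients: 6 × 45 = 270, of whom 270 × (1 - u) are one-dose. Dose 2 uptake u is not in the documents. For an assumed u of 50% to 90% this is 135 to 27.
- SAP Table 7 labels Cohort 1 as dosed once, although SAP Table 1 offers that cohort Dose 2 on consent. If all 45 Cohort 1 recipients were one-dose, the total is 45 + 225 × (1 - u), about 158 to 68, and the two Cohort 1 arms are treated alike. The imbalance then lies in Cohorts 2 to 4: 5 × 15 = 75 of 75 controls against about 113 to 23 of 225 BNT162b4 recipients.

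These are counts of people whom a list stops covering, not of people vaccinated.

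**How an outside vaccine between Day 170 and Visit 6 would be classed**
- Inclusion 6: a breach, hence a deviation under SAP 5.2.
- Protocol 6.5.1, 168 d reading: no longer on the prohibited list for a one-dose participant, so the SAP 5.2 example of prohibited medication does not clearly apply.
- SAP 5.1: the sample is dropped if the sponsor judges the deviation important and confounding.

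**Illustration of effect, on assumed inputs only.** If a fraction f of a group's Month 6 samples followed an outside vaccine and those titers rose F-fold, the geometric mean is multiplied by F^f. For F from 2 to 8 this gives 1.04 to 1.11 at f = 5%, 1.07 to 1.23 at 10%, and 1.15 to 1.52 at 20%. The documents support no particular f or F.

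**The case against.** The strongest reply is that the SAP already copes. A breach of inclusion 6 is a deviation by the SAP's own definition, SAP 5.2 names a closely similar case as its example of sample-level exclusion, and key deviations that exclude samples must be identified before database lock. Protocol 6.5.1 stops prohibiting but nowhere permits, so a site that keeps the stricter rule satisfies both sections. Footnote k of the schedule of activities also treats non-trial SARS-CoV-2 vaccination as prohibited medication with no 168 d limit. All of this stands. It shows which rule was probably intended and that exclusion is possible; it does not make exclusion certain.

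Four stronger readings are tempting, and the documents do not support them.
- A reader might infer that 6.5.1 is what makes exclusion depend on sponsor judgement. It is not: SAP 5.1 requires that judgement for every such deviation, and aligning 6.5.1 alone would leave it in place. The conflict only adds doubt about the classification.
- A reader might say that every in-window Visit 6 draw falls after the bar. That holds only on the 168 d reading.
- A reader might conclude that control Month 6 titers will be biased against the BNT162b4 groups. The documents give neither outside-vaccine uptake nor its titer effect, and each participant agreed under inclusion 6 not to be vaccinated before the last visit.
- A reader might extend the problem to the secondary endpoints. Those are at baseline and 28 d after each dose. The XBB.1.5 reference at Dose 2 comes from Dose 2 recipients, who stay barred.

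It is also fair to say that the visible part of SAP 6.6.1 itemises no Month 6 summary for controls. Table 7 does list those titers for the final report. Parts of the SAP's immunogenicity section are redacted, so a handling rule there cannot be excluded, although SAP 5.1 sets out the general exclusions and names none for outside vaccination.

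**Conclusion.** The contradiction is real and the point is minor. Protocol 6.5.1 states a shorter bar than the criterion it cites, and the shortfall falls on one-dose participants, who include all 90 planned controls. On the 168 d reading an outside vaccine could precede a valid Month 6 sample by at most 27 d (10 d at target); on the six-month reading, by at most 13 d (none at target). The SAP can remove such a sample because inclusion 6 is still breached, but removal is discretionary and the 6.5.1 wording makes it less predictable.

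The possible effect is confined to descriptive Month 6 titers, with no formal comparison planned, and its size cannot be derived from the documents. The primary safety endpoints do not use titers. The Day 28 secondary samples fall either well before Day 169 or in Dose 2 recipients, who remain barred. The conclusion assumes that the redacted text contains no rule on outside vaccination.

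**What to change.** Amend Protocol 6.5.1 so that non-trial COVID-19 vaccines are barred to the last trial visit for all Cohort 1 to 4 participants, as inclusion 6 already states.

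In SAP 5.1 and 6.6, next to the NAAT rule, add that samples taken after any non-trial COVID-19 vaccination are excluded from that visit onward in every arm, whether or not the vaccination is classed as a protocol deviation, and that the number excluded is reported by treatment group. This rule works even if 6.5.1 is not amended, and it removes the dependence on classification that the protocol change alone would leave.

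No new data are needed: SAP Table 10 has medication recorded without restriction at Visits 5 and 6, and SAP 6.3.2 already summarizes concomitant vaccinations. The cost is one protocol wording change, one SAP sentence and a few late samples. One-dose participants would wait at most 210 - 169 = 41 d longer than 6.5.1 states, which inclusion 6 already asks of them.

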7 DISCONTINUATION OF TRIAL TREATMENT AND TRIAL SUBJECT DISCONTINUATION/WITHDRAWAL

Any safety concerns of the investigators should be discussed with the sponsor immediately upon occurrence or awareness to determine if the trial subject should continue or discontinue trial treatment.

7.1 Discontinuation (stopping) or pausing (temporary halting) of trial treatment

The following pausing rules are established within the trial based on reported AEs, e-diary reactogenicity data, ECG findings, and clinical laboratory results.

Safety data will be reviewed on an ongoing basis by investigators and sponsor.

The sponsor will set up regular IRC meetings (as specified in the IRC Charter). In addition, *ad hoc* IRC meetings will be triggered by reported events that contribute to pausing rules (see Section 7.1.1).

If the sponsor confirms reported events fulfill pausing rules criteria:

- The IRC will review all related data.
- Randomization and trial treatment administration for the impacted cohort(s) will be paused until the IRC recommends that assignment to the cohort and administration of trial treatment may be resumed.

For all trial subjects who are vaccinated, all other routine trial procedures and assessments, including ongoing data entry, reporting of AEs, subject-reporting of reactogenicity in e-diaries, blood draws, and subject follow-up, will continue during the pause.

